#### 6.5.f. Pain.

- A Pain History will be obtained, including an assessment of painful bodily locations/distribution (with the Michigan Body Map), etiology of pain (if identifiable), duration, character and quality of pain, and aggravating and alleviating factors.
- The Graded Chronic Pain Scale (GCPS) is a 7-item questionnaire that measures pain intensity and interference over the last 1, 3, or 6 months. Scores can be used to classify participants on a Chronic Pain Grade: pain-free (grade 1), low disability and low intensity (grade 2), low disability, high intensity (grade 3), high disability, moderately limiting (grade 4), and high disability, severely limiting (grade 5).
- The Western Ontario and McMaster Universities Arthritis Index (WOMAC) is a well-validated and widely utilized measure of pain symptoms and physical disability. It is comprised of 24 items to evaluate three domains: pain, stiffness, and physical function. Responses can be summated for domain-specific scores, as well as a global score.
- The PainDETECT will be used to determine the presence of neuropathic pain.
- Movement-evoked pain (MEP) refers to the pain during activity, which is a primary driver of musculoskeletal pain. MEP will be assessed immediately after each physical task using a 101-point numerical rating scale, with 0 corresponding to “no pain” and 100 to “the most intense pain imaginable.”

**6.5.g. Disability.** The Pepper Assessment Tool for Disability (PAT-D) is a validated, 23-item instrument measuring 5 domains of function in older adults: mobility, transferring, upper extremity, activities of daily living (ADL), and instrumental activities of daily living (IADL).

#### 6.5.h. Physical function.

- The Short Physical Performance Battery (SPPB) is a widely used geriatric assessment designed to evaluate the physical performance and mobility of older adults. It consists of a series of simple tests that assess three major components: balance, gait speed, and lower extremity strength (chair stand test). Each component is scored on a scale

from 0 to 4, with higher scores indicating better performance. An SPPB of  $\leq 10$  is predictive of mobility disability and all-cause mortality.

- Handgrip strength test will be measured with a dynamometer. Handgrip strength is a measure of physical function and is suggested as a biomarker of aging. Maximal grip strength for each hand will be measured using a handheld dynamometer (Jamar, Lafayette Instruments, Lafayette, IN).
- The 6-minute walk test (6MWT) is a simple, inexpensive, sub-maximal exercise test commonly used to assess functional capacity and endurance in older adults. Participants are instructed to cover as much distance as possible in 6 minutes along a rectangular pathway. Normative data for 6MWT performance by age in older adults is available for comparison.

**6.5.i. Dietary intake.** Dietary intake data will be collected using the Diet History Questionnaire (DHQ), version III (2018). The DHQ-III is a freely available web-based, self-administered food frequency questionnaire consisting of 135 food and beverage items and 26 dietary supplement questions regarding the type, frequency, and serving sizes of foods, beverages, and dietary supplements consumed within the previous month.

#### **6.5.j. Cognitive function.**

- The Montreal Cognitive Assessment (MoCA) is a brief, 10-minute measure of global cognitive function and a screening tool for mild-to-severe cognitive impairment. The test assesses cognitive domains, such as attention, memory, orientation, language, conceptual thinking, and planning. Different versions of the MoCA will be used at each visit to minimize retest effects.
- The NIH Toolbox Cognition Battery (NIHTB-CB) is comprised of 7 tests that measure 8 abilities within 6 major cognitive domains: *executive function, episodic memory, language, processing speed, working memory, and attention*. Composite scores will be calculated for (1) fluid, (2) crystallized, and (3) global cognitive function. The toolbox takes approximately 30 minutes to complete and is administered with a tablet, facilitating administration and reducing data management burden.

#### **6.5.k. Other.**

- Acceptance of the intervention will be assessed with the Patient Global Impression of Change (PGIC) and the Medicine Acceptability Questionnaire (MAQ).
- Mood/affective factors will be assessed with the Fear Avoidance Beliefs Questionnaire (FABQ), Pain Self-Efficacy Questionnaire (PSEQ), Perceived Stress Scale (PSS), and the Geriatric Depression Scale-Short Form (GES-S).
- The Brief Pittsburg Sleep Quality Index (B-PSQI) will be used to assess sleep quality.

- Quality of life (QoL) will be assessed with the EuroQol 5 Dimension 5 Level (EQ-5D-5L).

**6.5.I. Sample size and statistical approach:** This pilot study is designed as a small-scale test to guide the design and implementation of large-scale studies to evaluate the effectiveness of krill oil supplementation among older adults with chronic musculoskeletal pain. We will enroll 40 older adults who will be randomly assigned (1:1) to either krill oil ( $n=20$ ) or placebo ( $n=20$ ) for a 3-month trial duration. Approximately 16 participants per group after a 20% loss to follow-up is expected to provide sufficient data to indicate the feasibility of a larger study and to provide descriptive estimates of effects. **Aim 1.** Feasibility and acceptability will be determined as (1) meeting at least 80% of the recruitment goal ( $n=32$ ), (2) no more than 20% attrition, and (3) treatment acceptance and adherence ( $\geq 70\%$  consumption of prescribed doses and increased blood  $\omega$ -3 index). **Aim 2.** Mean changes in  $\omega$ -3 index and  $\omega$ -6: $\omega$ -3 ratio will be evaluated with paired-samples T-tests for within-group difference and independent-samples T-tests for between-group difference. An intention-to-treat approach will be used for between-group analyses. While there is currently no guidance on what may constitute a minimal clinically meaningful change in plasma  $\omega$ -3 index, current evidence supports that an  $\omega$ -3 index  $\geq 8\%$  may be protective against cardiovascular disease whereas an index of  $\leq 4\%$  indicates increased risk. Similarly, an  $\omega$ -6: $\omega$ -3 ratio of 4:1 or lower is considered optimal for health. Baseline and 3-month levels of the  $\omega$ -3 index and the  $\omega$ -6: $\omega$ -3 ratio will be compared against these benchmarks. **Aim 3.** Due to the repeated-measures design, we will use mixed-effects linear regression models to evaluate changes in pain intensity and functional interference (WOMAC), as well as changes in objective measures of physical function (SPPB, 6MWT). Fixed effects will be specified for the treatment group, time (in weeks), and a group\*time interaction effect. An independence covariance matrix structure will be assumed with a random intercept for each participant included. A 20% pain reduction on a 0-10 numeric rating scale is considered a clinically significant pain reduction. A 1-point change in the SPPB and a 50-m increase in the 6MWT are considered clinically meaningful changes for older adults.

## 6.6. Adverse events:

**6.6.a. Definition of adverse events (AEs):** Adverse event means any untoward or unfavorable medical occurrence in a human subject, including any abnormal sign (e.g., abnormal physical exam or laboratory finding), symptom, or disease, temporally associated with the subject's participation in the research, whether or not considered related to the subject's participation in the research. Adverse events encompass both physical and psychological harms.

**6.6.b. Definition of serious adverse events (SAEs):** An adverse event or suspected adverse reaction is considered "serious" if, in the view of the investigators, it meets any of the following criteria:

- Results in death

- Is life-threatening (places the subject at immediate risk of death from the event as it occurred)
  - Requires inpatient hospitalization or prolongation of existing hospitalization
  - Results in a persistent or significant disability/incapacity
  - Results in a congenital anomaly/birth defect
  - Any other adverse event that, based upon appropriate medical judgment, may jeopardize the subject's health and may require medical or surgical intervention to prevent one of the other outcomes listed in this definition
- Examples of such events include allergic bronchospasm requiring intensive treatment in the emergency room or at home, blood dyscrasias or convulsions that do not result in inpatient hospitalization, or the development of drug dependency or drug abuse.

### 6.6.c. Classification of an adverse event

**6.6.c.1. Severity of event:** The following guidelines will be used to describe the severity of AEs

- **Mild** – Events require minimal or no treatment and do not interfere with the participant's daily activities.
- **Moderate** – Events result in a low level of inconvenience or concern with the therapeutic measures. Moderate events may cause some interference with functioning.
- **Severe** – Events interrupt a participant's usual daily activity and may require systemic drug therapy or other treatment. Severe events are usually potentially life-threatening or incapacitating. Of note, the term "severe" does not necessarily equate to "serious".

**6.6.c.2. Relationship to study intervention:** All AEs must have their relationship to the study intervention assessed by the Safety Monitor who examines and evaluates the participant based on temporal relationship and his/her clinical judgment. The degree of certainty about causality will be graded using the categories below. In a clinical trial, the study product must always be suspect.

- **Definitely Related** – There is clear evidence to suggest a causal relationship, and other possible contributing factors can be ruled out. The clinical event, including an abnormal laboratory test result, occurs in a plausible time relationship to study intervention administration and cannot be explained by concurrent disease or other drugs or chemicals. The response to withdrawal of the study intervention (dechallenge) should be clinically plausible. The event must be pharmacologically or phenomenologically definitive, with use of a satisfactory rechallenge procedure if necessary.
- **Probably Related** – There is evidence to suggest a causal relationship, and the influence of other factors is unlikely. The clinical event, including an abnormal laboratory test result, occurs within a reasonable time after administration of the study intervention, is unlikely to be attributed to concurrent disease or other drugs

or chemicals, and follows a clinically reasonable response on withdrawal (dechallenge). Rechallenge information is not required to fulfill this definition.

- **Potentially Related** – There is some evidence to suggest a causal relationship (e.g., the event occurred within a reasonable time after administration of the trial medication). However, other factors may have contributed to the event (e.g., the participant's clinical condition, other concomitant events). Although an AE may rate only as “possibly related” soon after discovery, it can be flagged as requiring more information and later be upgraded to “probably related” or “definitely related”, as appropriate.
- **Unlikely to be related** – A clinical event, including an abnormal laboratory test result, whose temporal relationship to study intervention administration makes a causal relationship improbable (e.g., the event did not occur within a reasonable time after administration of the study intervention) and in which other drugs or chemicals or underlying disease provides plausible explanations (e.g., the participant's clinical condition, other concomitant treatments).
- **Not Related** – The AE is completely independent of study intervention administration, and/or evidence exists that the event is definitely related to another etiology. There must be an alternative, definitive etiology documented by the clinician.

**6.6.c.3. Time period and frequency for event assessment and follow-up:** The occurrence of an AE or SAE may come to the attention of study personnel during study visits and interviews of a study participant presenting for medical care, or upon review by a study monitor.

Any medical condition that is present at the time that the participant is screened will be considered as baseline and not reported as an AE. However, if the study participant's condition deteriorates at any time during the study, it will be recorded as an AE.

The Safety Monitor will record all reportable events with start dates occurring any time after informed consent is obtained until 7 (for non-serious AEs) or 30 days (for SAEs) after the last day of study participation. At each study visit, the investigator will inquire about the occurrence of AE/SAEs since the last visit. Events will be followed for outcome information until resolution or stabilization.

**6.6.d. Reporting of AEs/SAEs:** Study progress and safety will be reviewed bi-weekly or more frequently by the principal investigator. Progress reports, including AEs will be provided to an Independent Monitoring Committee for bi-annual reviews. The Independent Monitoring Committee for this study will consist of an established board that reviews all studies conducted within the University of Florida's Pepper Center during bi-annual conference calls. This board is comprised of (1) [name]., Chair, epidemiologist, (2) [name]., biostatistician, and (3) [name]., physician/clinical researcher. An annual report will be compiled and will include a list and summary of AEs, and whether adverse event rates are consistent with pre-study assumptions.

The PI will immediately report to the sponsor any SAE, whether or not considered study intervention related, including those listed in the protocol, and must include an assessment of whether there is a reasonable possibility that the study intervention caused the event. All SAEs will be followed until satisfactory resolution or until the site investigator deems the event to be chronic or the participant is stable.

The study sponsor will be responsible for notifying the Food and Drug Administration (FDA) of any unexpected fatal or life-threatening suspected adverse reaction as soon as possible, but in no case later than 7 calendar days after the sponsor's initial receipt of the information. In addition, the sponsor must notify FDA and all participating investigators in an Investigational New Drug (IND) safety report of potential serious risks, from clinical trials or any other source, as soon as possible, but in no case later than 15 calendar days after the sponsor determines that the information qualifies for reporting.

**6.6.e. Reporting events to participants:** In the case that adverse events are identified from blood chemistry tests, participants will be immediately notified by the investigators.

**6.7. Participant discontinuation/withdrawal from the study:** Participants are free to withdraw from participation in the study at any time upon request. The investigators may discontinue or withdraw a participant from the study for the following reasons:

- Significant study intervention non-compliance
- If any clinical adverse event (AE), laboratory abnormality, or other medical condition or situation occurs such that continued participation in the study would not be in the best interest of the participant
- Disease progression which requires discontinuation of the study intervention
- If the participant meets an exclusion criterion (either newly developed or not previously recognized) that precludes further study participation
- Participant unable to receive krill oil for 12 weeks

Subjects who sign the informed consent form and are randomized but do not receive the study intervention may be replaced. Subjects who sign the informed consent form, and are randomized and receive the study intervention, and subsequently withdraw, or are withdrawn or discontinued from the study, will not be replaced.

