**Table 2. Inclusion and Exclusion Criteria**

| Inclusion   |
|---|
| 
 
• Provision of signed and dated informed consent form
 
• Stated willingness to comply with all study procedures and availability for the duration of the study
 
• Male or female, aged <math>\geq 60</math> years
 
• Exhibiting chronic musculoskeletal pain of the hip, knees, or lower back (<math>>3</math> months)
 
• Average pain <math>\geq 4</math> on a 0–10 numeric rating scale
 
• Exhibiting moderate mobility limitations (Short Physical Performance Battery score 4-10)
 
• Ability to take oral supplement and be willing to adhere to the supplementation regimen
 
• Agreement to adhere to Lifestyle Considerations (see section 6.4.d) throughout study duration
 
  |
| Exclusion   |
| 
 
• Any known coagulation or bleeding disorders
 
• Standing regimen of anticoagulants or full-dose aspirin
 
• Regular use of opioids or high-dose NSAIDs
 
• Taking medication known to affect muscle (e.g. steroids)
 
• Taking selective serotonin reuptake inhibitors (SSRIs)
 
• Omega-3 supplementation within the past 3 months
 
• High consumption of fatty fish (<math>>2</math> servings/week)
 
• Habitual supplementation with other complementary medicines/supplements that may affect the study results, including St. John's Wort
 
• Known allergy to seafood
 
• Clinically significant conditions: uncontrolled diabetes, severe cardiovascular disease, seizure disorders, uncontrolled hypertension (<math>>150/90</math>mmhg at baseline), cancer or cancer that has been in remission <math><5</math> years
 
• History of atrial fibrillation or atrial flutter
 
• Dementia
 
• History of smoking, alcohol abuse, or illicit drug use
 
• Ambulatory impairments which would limit the ability to perform physical function tests
 
• Treatment with another investigational drug or other intervention within 3 months
 
• Planning a surgical procedure during the study period
 
• Planning to permanently leave the area during the study period
 
 |

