| Weight  | X                    | X                       |                               | X                         |                             | X                        |
| Waist circumference   |                      | X                       |                               | X                         |                             | X                        |
| Physical Performance                                       |                      |                         |                               |                           |                             |                          |
| Short Physical Performance Battery (SPPB)                         | X                    |                         |                               | X                         |                             | X                        |
| Handgrip strength   |                      | X                       |                               |                           |                             | X                        |
| 6-minute walk test (6MWT)   |                      | X                       |                               |                           |                             | X                        |
| Whole blood collection                                     |                      | X                       |                               | X                         |                             | X                        |
| Dried blood spot (OmegaQuant)                                     |                      | X                       |                               | X                         |                             | X                        |
| CMP, CBC (safety), lipids, hs-CRP                                 |                      | X                       |                               | X                         |                             | X                        |
| Inflammatory markers (IL-6 and TNF- $\alpha$ )                    |                      | X                       |                               |                           |                             | X                        |
| Questionnaires   |                      |                         |                               |                           |                             |                          |

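### Protocol section 6.7 allows withdrawal from the study for product-related reasons and has no capsule-stop-only option, so it can create avoidable missing outcomes and use up the attrition allowance

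*Protocol*

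**What the plan says.** Protocol section 6.7 treats leaving the product and leaving the study as one event: "The investigators may discontinue or withdraw a participant from the study for the following reasons". Three of its five reasons concern the product: "Significant study intervention non-compliance", "Disease progression which requires discontinuation of the study intervention" and "Participant unable to receive krill oil for 12 weeks". The level of non-compliance that counts as significant is not defined.

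The other two reasons concern participation itself. One is an adverse event or other condition that makes staying in the study against the participant's interest. The other is "If the participant meets an exclusion criterion (either newly developed or not previously recognized) that precludes further study participation".

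Participants who have received product and "subsequently withdraw, or are withdrawn or discontinued from the study, will not be replaced". The only follow-up described after participation ends is safety follow-up: event recording for 7 days (30 for serious events) in section 6.6.c.3, and following serious events to resolution in 6.6.d.

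The SAP analyses all randomized participants as assigned, whatever their adherence. It uses maximum likelihood under missing at random and offers an optional per-protocol subset with at least 70% adherence. Attrition is part of the primary feasibility objective. The limit is at most 20% in protocol sections 5 and 6.5.l and in the SAP, but below 20% in protocol Table 1.

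**The concern.** A participant who stops taking capsules can usually still walk, fill in a WOMAC and give blood. If section 6.7 is applied, that person leaves the study and the later outcomes are lost for a reason that has nothing to do with whether they could be measured. The SAP's analysis depends on having those outcomes, and its optional per-protocol subset presumes that poor adherers otherwise contribute data.

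The primary objective is also affected. Attrition is meant to show whether older adults with chronic pain can be kept in a 3-month trial. If capsule stops are recorded as withdrawals, the attrition figure mixes product tolerance with retention, and the team could conclude that retention failed when participants were willing to return.

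**Working it through.** **1. Which outcomes are lost (protocol Table 3).** The 6-minute walk is measured at baseline and Final only, so withdrawal at any time before Final leaves no post-baseline value. SPPB, WOMAC and the omega-3 index also have a week-6 value, so withdrawal after week 6 loses only week 12.

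**2. The plan's own figures.** 20 × (1 − 0.20) = 16 per group and 0.80 × 40 = 32. Both reproduce section 6.5.l.

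**3. The attrition allowance.**
- At most 20% of 40: 0.20 × 40 = 8 losses allowed.
- Below 20% of 40 (Table 1): 7 losses allowed.
- Each withdrawal is 1/40 = 2.5 percentage points. Withdrawing 10% for product reasons takes 4 of the 8.

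**4. Chance of missing the criterion.** Let X be the number lost, binomial with n = 40 and true loss rate p. The criterion is missed when X > 8, or X > 7 under Table 1. The documents give only the planning figure of 20% total loss, so p is an assumption shown over a range.

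| Assumed true loss p | P(X > 8), at most 20% | P(X > 7), below 20% |
|---|---|---|
| 10% | 1.5% | 4.2% |
| 15% | 13.5% | 24% |
| 20% | 41% | 56% |
| 25% | 70% | 82% |

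If capsule stops counted as attrition add 5 points to a 10% loss, the chance of missing goes from 1.5% to 13.5% (4.2% to 24% under Table 1). If they add 5 points to a 15% loss, it goes from 13.5% to 41% (24% to 56%).

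**5. Variance and treatment estimates.** Simulations assumed that half of those whose week-12 change fell below the placebo 5th, 10th or 20th percentile were withdrawn.
- With no treatment effect, within-person variance was understated by at most about 15% (6-minute walk, 20% cut-off). The relative standard error of a variance on 30 degrees of freedom is √(2/30) = 26%.
- With a true effect of 0.5 SD, the estimate was biased by at most 0.06 SD. The pilot's standard error is √(2/20) = 0.32 SD with 20 per arm, or √(2/16) = 0.35 SD with 16.
- That bias depends on placebo losing more people than krill oil (10% against 4.5% at the 20% cut-off), which nothing in the documents supports.

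**The case against.** **Discretion and intent-to-treat.** Withdrawal is at the investigator's discretion, so loss is possible, not certain. A reader might infer that section 6.7 contradicts the SAP's intent-to-treat analysis. It does not: a withdrawn participant's earlier values stay in the mixed model under the assigned arm. What stands is narrower. The rule produces missing later values that could have been collected, and the result then leans on missing at random.

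**The list of reasons.** The newly met exclusion applies only where it precludes further participation, so it is not a product-only reason. One such exclusion, "Ambulatory impairments which would limit the ability to perform physical function tests", bears on the outcome tests, but others, such as dementia or permanently leaving the area, may make a week-12 visit unreliable or impossible. This ground should stay. The 12-week reason is ambiguous: read as 12 weeks without product, it could hardly apply before Final. Progression severe enough to require stopping a supplement may be rare. Non-compliance is the ground most likely to matter.

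**Attrition.** Counting investigator withdrawals as attrition is a defensible, conservative choice. But the documents do not say that they make it, and the two thresholds allow different numbers of losses.

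**Future design.** A reader might also infer that the rule would distort the variance estimates or sample size of the future trial. The documents do not support that. The loss mechanism is assumed, the effects lie within random error, and the net effect on sample size can go either way. Protocol section 5 itself says that pilots cannot adequately provide effect sizes.

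**Conclusion.** The point holds as a design matter to consider. Section 6.7 allows study withdrawal for three product-related reasons and offers no capsule-stop-only path. When used, it removes outcomes the SAP wants and, with attrition undefined, can count willing participants against a primary criterion.

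The size that can be defended is the attrition arithmetic: 8 (or 7) allowed losses of 40, and a chance of missing the criterion that rises from 1.5% to 13.5% to 41% (4.2% to 24% to 56% under Table 1) as true loss goes from 10% to 15% to 20%. These percentages rest on assumed loss rates and independent losses. How often investigators would use the rule is unknown. The variance, bias and sample-size effects should carry no weight in the decision.

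**What to change.** Amend section 6.7 so that significant non-compliance, progression that requires stopping the intervention, and inability to take the product lead only to stopping capsules. These participants keep the scheduled week-6 and week-12 assessments unless:

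- consent is withdrawn;
- the adverse-event or best-interest ground applies;
- an exclusion truly precludes participation; or
- a specific test is unsafe for that person, in which case only that test is skipped.

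Define attrition as loss of the week-12 assessment, and use one threshold throughout (at most 20%, or below 20%). Report capsule stops separately by arm and reason. Analyse all observed values under intent-to-treat, as the SAP already intends.

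The cost is about two sentences of protocol text, with no new visits or procedures. Staff will need some effort to bring back people who have stopped capsules. Week-12 means will include off-product participants and may look slightly less favourable. The change will not recover a 6-minute walk from someone who cannot walk safely, but it keeps WOMAC, the omega-3 index and any test that person can do.
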